1. Baduanjin qigong is more effective than no-intervention control in (i)reducing cancer-related symptoms and symptom distress, (ii)improving mental health, (iii)enhancing quality of life, (iv)positively altering biomarkers, (v)enhancing mindfulness level.

- 2. Mindfulness meditation is more effective than no-intervention control in similar areas and directionality as the above (i) to (v).
- 3. There would be commonalities and differences between Baduanjin qigong and Mindfulness meditation in a)type of outcome variables, b)magnitude of change, c)time when significant outcomes emerge, d)frequency and length of self-practice and long-term compliance.
- 4. The associations among physical and psychological variables as well as psychophysiological biomarkers and the changes of such associations across the time points are exploratory.

Research Plan and Methodology

Research design

This study will utilize a 3-arm randomized controlled trial design with waitlist control. A conceptual model is provided in Appendix A. Upon recruitment, participants will be screened according to the inclusion and exclusion criteria (Appendix B). Baseline data will then be collected. Subsequently, eligible participants will be randomly assigned into one of the 8-week (i)Baduanjin qigong group, (ii)Mindfulness meditation group, and (iii)Waitlist Control group. The Waitlist Control group will continue to receive routine medical care and will have the option to attend either of the interventions after the study is completed. Participants from all 3 arms will be assessed on 4 time points (i)baseline prior randomization, (ii)mid-intervention (4th week), (iii)post intervention (8th week), (iii)6 months post-intervention. Participants will complete the study in 8 months.

Sample size determination, Participant eligibility and Recruitment

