To achieve a statistical power of 0.8 with medium effect size (f2 = 0.25) and significance level of 0.05 in repeated measures MANOVA under the proposed 3-group, 4-time point design, a sample size of 126 is needed. Assuming an attrition rate of about 33.5%, based on prior trials on cancer patients using qigong[8], recruitment of 189 participants (63 per arm) is required. The study population will consist of 189 Chinese-speaking patients aged between 18 and 74, diagnosed with colorectal cancer. Participants will be recruited via posters and newsletters put up at hospital and community organizations servicing cancer patients including Hong Kong Anticancer society. Recruitment will also be done via referral from oncologists. Screening will be conducted after recruitment by a trained research assistant or by the referring medical professional based on the inclusion and exclusion criteria listed in Appendix B.

Intervention groups

Both intervention groups will consist of 8 weekly 90-minute sessions, with a total of 12 contact hours. Interventions will be held in groups of about 10 participants led by 2 trainers qualified for the respective intervention form, one of whom will also be a mental health professional.

a) *The Baduanjin qigong Intervention*[61] consist of eight sequential forms of movements which is practiced with guidance on rhythmic breathing and mindful awareness (see Appendix C for details). Each cycle of the eight movements requires 10 to 15 minutes for completion. Four

cycles will be practiced in each session with short breaks arranged between them. In addition to the in-session practices, participants are encouraged to practice Baduanjin qigong for at least 20 minutes each day and keep a record of their daily practice in a log book.

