1. Effectiveness of Baduanjin qigong and Mindfulness meditation (Objective 1 & hypotheses 1&2)

Analysis of variance and chi-square independence tests will be carried out using SPSS to compare the demographic profile of the three groups. The study will use latent growth modeling (LGM) in Mplus 7 [71] to explore the effectiveness of the two mind-body interventions over the four assessment time points, between the respective experimental and waitlist control groups. Traditional analytic techniques such as ANOVA or MANOVA adopt traditional deletion or substitution methods and may not yield precise estimates in the presence of missing data. LGM flexibly analyzes the overall population trajectories using nonlinear modeling such as quadratic growth and the between-person variation in outcome variables, thus allows analysis of all available data via full information maximum likelihood under missing-at-random assumption. This matches the standard intent-to-treat analytic approach of clinical trials with missing data. The level of statistical significance is set at p=0.05, with p-values greater than 0.05 but smaller than 0.10 taken as marginal significance. All models are estimated using the robust maximum likelihood estimator.

2. Commonalities and Differential effectiveness for Baduanjin qigong and Mindfulness meditation (Objective 2 and hypothesis 3).

To examine the commonalities and differential effectiveness for Baduanjin qigong and Mindfulness meditation, treatment effects of the two interventions are directly compared in multigroup conditional growth models. The linear slope factors of the outcomes are contrasted across the two intervention groups via computing the difference in the intercepts of the slope factors between two groups using Model Constraint option. Demographic and clinical characteristics that differed significantly across the three groups in the preliminary analysis are entered as covariates. Influential confounding variables such as clinical prognosis or frequency, intensity and duration of maintenance (compliance) of practice will be controlled.

3. The Mind-body correlations reflected in symptoms and psychophysiological markers (Objective 3 and hypothesis 4).

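### The plan does not say that the arms' baseline means are held equal in the growth models, or that the baseline outcome is adjusted for, so precision available from a pre-randomisation baseline may be lost

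*Combined protocol and SAP*

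**What the plan says.** Research design lists the assessments as "i)baseline prior randomization, (ii)mid-intervention (4th week), (iii)post intervention (8th week), (iii)6 months post-intervention". Baseline is therefore collected before allocation.

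In Data analyses, item 1 uses latent growth modelling "between the respective experimental and waitlist control groups". It allows nonlinear shapes such as a quadratic, but it names no parameter or contrast as the treatment effect.

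Item 2 is more specific: "treatment effects of the two interventions are directly compared in multigroup conditional growth models", with the linear slope factors contrasted "via computing the difference in the intercepts of the slope factors between two groups using Model Constraint option".

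Item 2 also sets the covariates: "Demographic and clinical characteristics that differed significantly across the three groups in the preliminary analysis are entered as covariates". A further sentence adds: "Influential confounding variables such as clinical prognosis or frequency, intensity and duration of maintenance (compliance) of practice will be controlled".

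Neither covariate sentence names the outcome's own baseline value. Nothing is said about whether the intercept-factor means are free or equal across arms, or about the time scores.

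**The concern.** Because baseline precedes randomisation, the three arms share one expected baseline mean by design. An analysis that uses this fact gains precision without further data. In a multigroup growth model with group-specific growth-factor means, each arm has its own intercept mean unless an equality is written. The plan goes as far as naming the Mplus option and the parameter to difference, yet it gives the analyst no instruction to write that equality. Two analysts could follow the text faithfully and report different estimates and p-values.

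If the means are free, the slope contrast ignores information about the outcome at time 0. It is also negatively correlated with the chance baseline difference, so the arm that happens to start worse tends to look as if it improved more. The trial is small, expects about a third of participants to be lost, and treats p-values between 0.05 and 0.10 as marginally significant, so modest shifts can change what is reported.

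**Working it through.** **Inputs from the documents.** 189 recruited, 63 per arm; attrition 33.5%; visits at baseline, week 4, week 8 and 6 months after the intervention. The plan's 126 before attrition is a repeated measures MANOVA calculation, so it offers no precision figure for the slope contrast to reproduce. For the attrition step, 126/3 = 42 completers per arm, and 126/(1 − 0.335) = 189.5, close to the stated 189.

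**Assumptions, because the plan gives no value.** The last visit is at about week 34 (8 + 26). Outcome SD is 1 at every visit. The correlation ρ between any two visits is equal, at 0.4 to 0.7. Data are complete unless stated. Time scores t are either calendar (0, 4, 8, 34) or equally spaced (0, 1, 2, 3).

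**Step 1: variance of the slope difference between two arms.**
- Baseline means free: 2(1 − ρ)/(nS), with S = Σt² − (Σt)²/4.
- Baseline means equal: 2(1 − ρ)/(n[Σt² − a(Σt)²]), with a = ρ/(1 + 3ρ).
- Ratio, equal to free: S/[Σt² − a(Σt)²]. The sample size cancels.

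Calendar scores: Σt = 46, Σt² = 1236, S = 1236 − 2116/4 = 707. Equal spacing: Σt = 6, Σt² = 14, S = 14 − 36/4 = 5.

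| ρ | a | Calendar ratio | Cut | Equal-spacing ratio | Cut |
|---|---|---|---|---|---|
| 0.4 | 0.182 | 707/851.3 = 0.831 | 17% | 5/7.455 = 0.671 | 33% |
| 0.5 | 0.200 | 707/812.8 = 0.870 | 13% | 5/6.8 = 0.735 | 26% |
| 0.7 | 0.226 | 707/758.2 = 0.932 | 7% | 5/5.871 = 0.852 | 15% |

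With dropout spread evenly from 63 to 42 per arm (7 lost before each follow-up visit), generalised least squares gives calendar cuts of 14%, 11% and 5%.

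**Step 2: power (calendar scores, complete data).** A two-sided 5% test with 80% power has expected z = 1.960 + 0.842 = 2.802. After a variance cut c, power is Φ(2.802/√(1 − c) − 1.960).
- ρ = 0.4: 2.802/√0.831 = 3.074, power 87%.
- ρ = 0.7: 2.802/√0.932 = 2.902, power 83%.

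**Step 3: dependence on the realised baseline imbalance (means free).** The imbalance has standard error √(2/63) = 0.178 SD. The chance that two arms differ by more than 0.2 SD is 2[1 − Φ(0.2/0.178)] = 0.26. Per 1 SD of imbalance, the slope-implied difference at the last visit T moves by −T(1 − ρ)t̄/S. With calendar scores this is −34 × 11.5(1 − ρ)/707 = −0.553(1 − ρ). An imbalance of 0.2 SD then gives:
- ρ = 0.4: 0.553 × 0.6 × 0.2 = 0.066 SD.
- ρ = 0.7: 0.553 × 0.3 × 0.2 = 0.033 SD.

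With a common baseline mean this dependence is zero. Averaged over randomisations, the free-means contrast has no bias (mean −0.0005 SD in 20,000 simulated trials with ρ = 0.5).

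**Step 4: how much of the slope gain is baseline adjustment.** Adjusting the slope contrast only for the observed baseline difference cuts its variance by (1 − ρ)t̄²/S = (1 − ρ) × 132.25/707, which is 11% at ρ = 0.4 and 6% at ρ = 0.7. The rest of the 17% to 7% comes from making the fitted straight lines share an origin. For a change to a single visit such as week 8, the ratio is (1 − ρ²)/[2(1 − ρ)] = (1 + ρ)/2, a cut of 30% to 15%. The plan does not name that contrast.

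**Step 5: effect of the constraint on a misfitting line.** Suppose the true differences at the four visits are 0, 0.25, 0.5 and 0.5 SD. The free straight-line fit implies a week-34 difference of 0.37 SD. The same line with equal intercepts implies 0.46 SD at ρ = 0.4 and 0.40 SD at ρ = 0.7.

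**The case against.** The strongest reply is that nothing invalid has been shown. Several stronger readings are tempting, and the documents do not support them.

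- **That the plan frees the baseline means.** It is silent. A multigroup conditional model with a slope contrast by Model Constraint is compatible with equal intercept means. The supportable statement is that the equality is not written.
- **That baseline imbalance biases the effect.** It does not, over randomisations. The shift is conditional on the imbalance that occurs, and the standard error already includes it. The matter is efficiency, not validity.
- **That the shift is as large as for a change score.** For a single-visit change, a 0.2 SD imbalance gives (1 − ρ) × 0.2 = 0.12 to 0.06 SD. The named contrast is the linear slope, for which calendar scores give 0.07 to 0.03 SD even at week 34.
- **That every test under Objectives 1 and 2 is affected.** Extended compliance is practice duration and has no pre-randomisation value to hold equal. For the waitlist comparisons no contrast is given, so the gap there is one of specification.
- **That one equality constraint settles it.** Step 5 shows that the bare constraint on a straight line can itself move the estimate. The growth shape has to be settled at the same time.

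All of these limits stand. What remains is that a baseline value already collected before randomisation is not put to use in the written analysis, and that using it costs little.

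**Conclusion.** The point holds as an inexpensive improvement in precision and a gap in specification. It does not show bias or an inflated error rate. The gain in the named slope contrast ranges from small (7% of variance, calendar scores, ρ = 0.7) to substantial (33%, equally spaced scores, ρ = 0.4), and it is somewhat less with dropout. The plan states neither time scores nor correlations, so no single figure can be fixed. These slope figures also assume that a straight line fits. Once post-baseline means are freed, as recommended below, the gain depends on the contrast chosen: 11% to 6% for a calendar-scored slope adjusted for baseline, and 30% to 15% for change to one visit. It is worth amending before the data are analysed.

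**What to change.** For each outcome measured before randomisation (not compliance), fit one model to all three arms, with time 0 at baseline and the baseline mean held equal across arms. Adjusting for the baseline outcome is the equivalent alternative once post-baseline means are free. State the time scores. Let the post-baseline means be free or piecewise, so that the constraint acts on the baseline itself and not on a fitted line. Take qigong–waitlist, mindfulness–waitlist and qigong–mindfulness from this one model with Model Constraint, so that the three estimates are coherent and the waitlist contrasts are defined.

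The cost is a short rewrite of items 1 and 2 of Data analyses, plus specifying and checking the growth form for each outcome. That is more than one line of code, but it needs no new data, participants or visits.

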- (f) Salivary cortisol. Salivary cortisol collection will be conducted by participants themselves. Saliva samples will be collected at 5 prescribed times (awakening, 45 minutes postawakening, 12:00pm, 5:00pm and 9:00pm) using the collection device, Salivette, which includes a cotton swab to place under the tongue. Smoking, eating and drinking should be avoided and refrained one hour prior to saliva collection. Samples collected will be kept frozen at -20°C.Daily condition measures with salivary cortisol-Measures on participants' health behaviors and activities on the day of saliva collection will be collected along with cortisol. These include (i)sleep quantity that day (hours of sleep at night and nap hours), (ii)subjective sleep quality rated on a scale of 1-10, (iii)smoking habit and the number of cigarettes that day (iv)alcohol/coffee drinking habit and the approximate amount that day, and (v)subjective evaluation of stress levels on the day of collection rated on a scale of 1-10. All the above measures will affect the diurnal cortisol rhythm and must be considered in analysis.
- (g) Blood pressure and heart rate. Following recommended procedures by the Canadian Medical Association[69], blood pressure and heart rates would be measured twice from each arm with a five minute rest intervals between measurements. The four collected readings will be averaged.
- (h) Mindfulness. The Chinese Five Facet Mindfulness Questionnaire (Short form) will be used upon permission. It has 5 domains, observing, describing, acting with awareness, nonjudging to inner experience and nonreacting to inner experience[70]. The 5-point Likert scale has 20 items.

- (i) Compliance. Participants will record their daily duration of qigong or mindfulness meditation practice over the course of the study. This will provide information on the frequency and intensity of practice, and maintenance of self-practice habits after the intervention period.
- (j) Demographics. Participants socio-demographic, such as age, gender, education level, employment status and marital status, as well as clinical profile, including cancer diagnosis, staging, treatment and medication record, onset of mood disturbances if any, critical events around the time of onset, physical exercise habits, complementary treatment used, and psychosocial support service utilization, will be documented based on self-report.

Data analyses

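### Objective 2 covariates are chosen by significance tests between randomised arms, which select by chance rather than prognosis, and no baseline covariate is fixed in advance

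*Combined protocol and SAP*

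**What the plan says.** In Data analyses, part 1, the three arms are first compared at baseline: "Analysis of variance and chi-square independence tests will be carried out using SPSS to compare the demographic profile of the three groups". Part 2, on the direct comparison of the two interventions, uses the result to build the model: "Demographic and clinical characteristics that differed significantly across the three groups in the preliminary analysis are entered as covariates". The only threshold given is the general one: "The level of statistical significance is set at p=0.05, with p-values greater than 0.05 but smaller than 0.10 taken as marginal significance".

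A second commitment follows directly: "Influential confounding variables such as clinical prognosis or frequency, intensity and duration of maintenance (compliance) of practice will be controlled". It lists no variables, coding or selection rule for clinical prognosis.

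The candidate variables are in Measurements, item (j), beginning "Participants socio-demographic, such as age, gender, education level, employment status and marital status, as well as clinical profile, including cancer diagnosis, staging, treatment" and ending "physical exercise habits, complementary treatment used, and psychosocial support service utilization, will be documented based on self-report". Under Research design, the first assessment is "i)baseline prior randomization", and only afterwards are patients allocated: "eligible participants will be randomly assigned into one of the 8-week" groups. Part 1 names no covariates for the comparisons with waitlist.

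**The concern.** Baseline is measured before a random allocation, so any difference between arms arises by chance. A test of that difference carries no information about whether the variable predicts outcome. A strong predictor with a modest imbalance stays out, while an irrelevant item that happens to reach p<0.05 goes in.

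Three further features weaken the rule:

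- Selection uses a three-arm test, but the estimate is a difference in slopes between two arms. A variable can enter because only the waitlist arm is unusual, and an imbalance between the two compared arms can be missed.
- The tests are described for the demographic profile, yet the rule draws on clinical characteristics as well.
- The plan does not say whether a variable with p between 0.05 and 0.10 counts.

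At stake are precision in a primary comparison that expects 33.5% attrition, and a model that can be written down before the arms are compared.

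**Working it through.** The plan gives no figure on this point to reproduce. Inputs from the documents: three arms, 126 evaluable participants (126/3 = 42 per arm), 189 recruited (63 per arm), significance level 0.05. Item (j) yields about 13 characteristics: five demographic and about eight clinical, with treatment and medication record counted as one. Independence between characteristics, the covariate-outcome correlations r and the effect size are assumptions.

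**1. How often the rule admits anything.** Each variable enters with probability 0.05.

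- 13 characteristics: expected number 13 × 0.05 = 0.65; P(at least one) = 1 − 0.95^13 = 0.49.
- Five demographic items only: 1 − 0.95^5 = 0.23.
- Sensitivity to the count: 0.40 with 10, 0.54 with 15.
- If marginal p-values also count: 1 − 0.90^13 = 0.75.

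**2. Mismatch between test and contrast.** At 42 per arm the standard error of a standardised difference between two arms is √(2/42) = 0.218. The chance that a covariate differs by more than 0.3 SD between the two intervention arms is therefore P(|Z| > 0.3/0.218) = 0.17. In simulation about 80% of such imbalances were not flagged by the three-arm test. At 63 per arm the figures are about 9–10% and about 70%. If the waitlist mean lies midway between the other two, the large-sample three-arm statistic equals z² and must exceed 5.99. An imbalance of up to z = √5.99 ≈ 2.4 then goes unadjusted.

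**3. Precision forgone.** Adjusting for one covariate multiplies the variance by 1 − r², which is worth 1/(1 − r²) − 1 more patients:

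- r = 0.2: 1/0.96 − 1 = 4%
- r = 0.3: 1/0.91 − 1 = 10%
- r = 0.5: 1/0.75 − 1 = 33%

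**4. Power.** This comes from a simulation of a two-arm contrast inside a three-arm trial, with 8,000 runs per setting and an assumed standardised difference of 0.5. It uses a simple mean comparison, not the full growth model.

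| Per arm | Covariates | No adjustment | Plan's rule | Prespecified |
|---|---|---|---|---|
| 42 | one, r = 0.3 | 0.62 | 0.62 | 0.66 |
| 42 | one, r = 0.5 | 0.61 | 0.61 | 0.73 |
| 42 | four, r = 0.3 each | 0.62 | 0.63 | 0.79 |
| 63 | one, r = 0.3 | 0.80 | 0.80 | 0.84 |
| 63 | one, r = 0.5 | 0.79 | 0.79 | 0.89 |
| 63 | four, r = 0.3 each | 0.81 | 0.81 | 0.93 |

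The rule performs almost as if there were no adjustment.

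**5. Type I error.** With no true difference, the rule rejected in 0.038 to 0.046 of runs across the settings simulated (Monte Carlo standard error √(0.05 × 0.95/8,000) ≈ 0.002). It is not inflated.

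**The case against.** The best defence is that the rule is not the whole adjustment. The sentence after it commits to controlling clinical prognosis without any test. The baseline value of each outcome is already one of the four time points in the growth model. For cortisol, Measurements item (f) requires same-day sleep, smoking, alcohol or coffee, and stress to be considered, again without a test. All of this stands. A reader might infer that the plan as a whole leaves prognostic variables out, and the documents do not show that. They show a promise with no variable attached, in an open-ended list whose other examples are practice behaviour after randomisation. That does not repair the rule.

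Three other inferences are tempting and unsupported:

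- **That the rule produces false positives.** Given a particular unadjusted imbalance, the error rate does rise. At r = 0.5 it is about 8% for z = 1.5 and 12% for z = 1.9, but at r = 0.2 it is only 5.6% and 6.2%. Those cases also presume a two-group selection test, which is not the plan's. Over all randomisations the error stays below 5%.
- **That covariates could be chosen to suit the outcome.** The rule looks only at baseline data, so this sentence does not permit it.
- **That the loss is a third of the sample.** That needs r = 0.5. The relevant correlation is with rate of change, and nothing in the documents supports so high a value for age, gender or stage.

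**Conclusion.** The point holds for objective 2. This part of the adjustment set is decided by chance and by a test on the wrong number of arms, and the adjacent promise on clinical prognosis is too vague to replace it. The consequence is loss of precision and of prespecification, not bias in the overall error rate. The probability of an arbitrary covariate entering depends on the count of candidates and on independence. The size of the precision loss depends entirely on an assumed correlation, so it should be read as a range from small to moderate. The defect does not invalidate the trial, but it should be corrected because a better rule is available from data already planned.

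**What to change.** In Data analyses, part 2, delete the significance rule. Before unblinding, define clinical prognosis as a short named list of baseline variables already collected, for example age, gender and staging, with their coding. Enter them in every objective 2 model, and preferably in the objective 1 models too, whatever the baseline p-values. Keep the baseline table descriptive. Time since main treatment appears only as an eligibility window in Appendix B and is not named in item (j); it can be added if the date recorded for eligibility is kept.

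Hold covariate effects equal across arms. Otherwise the difference in slope-factor intercepts is the treatment effect only where the covariates equal zero, and the parameter count grows. With age (1 term), gender (1) and four stages (3), each acting on an intercept and a linear slope, equal effects cost 5 × 2 = 10 parameters. Free effects cost 20 for two arms and 30 for three, which is heavy at 42 evaluable per arm. Coding stage as one ordered score reduces the equal-effects cost to 3 × 2 = 6. Otherwise the change is to wording only.

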In Traditional Chinese medicine, both movement-based and mind-based mind-body practices are known to have homeostatic functions to balance dysfunctional bodily systems. Examining the effects of mind-body practices on circadian cortisol rhythm may shed light on the homeostatic effect of mind-body practices on the dysregulation of the HPA system.

Clinical contributions

The clinical popularity of qigong and mindfulness meditation among local cancer survivors calls for a need for more established evidence on their benefits. Better understanding on culturally popular interventions, in particular, the common and unique effectiveness of different approaches are crucial, as patients and qualified healthcare professionals can select or provide practices which will produce maximum benefits, satisfaction, adherence, and sustainability. This study envisions bringing forth evidence-based mind-body practices which are easily learned, can be self-practiced and incorporated into patients' lifestyles.

Objectives

1. **Primary objective 1** is to study the effectiveness of Baduanjin qigong and Mindfulness mediation for Chinese colorectal cancer (CRC) patients as compared to a no-intervention control independently on:

(1) cancer-related symptoms and symptom distress

(2) mental health

(3) quality of life

(4) biomarkers

(5) mindfulness level

2. **Primary objective 2** is to examine the commonalities and differential effectiveness between two interventions on:

(1) outcome variables

(2) magnitude of change

(3) pace of change

(4) extended compliance

3. **Secondary objective** is to examine the associations between psychological, physical and psychophysical markers and how those relationships change across the time points.

Background of the research

The Reciprocity of the Mind and Body in Cancer

Colorectal cancer impairs patients on multiple levels of well-being. While most physical symptoms can be managed by medication, psychosocial stressors may arise and persist to complicate survival and reduce quality of life of survivors[19]. Patients, especially those who requiring colostomy, suffer from psychosocial trauma including depression, the fear of relapse, altered self-image, loss of social functioning and connections[20]. Local statistics further indicated a high prevalence of elevated depressive symptoms (21.8%)[21].

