(b) *The Mindfulness meditation Intervention* which has been used by co-Is ([name] and [name]) in previous studies is developed based on the core components of the established Mindfulness-Based Stress Reduction and the Mindful Self-Compassion program with adaptation for local practice[57, 62]. The focus of the group is to nurture mindful awareness, acceptance, and self-compassion. The group sessions are composed of a combination of mindfulness-based practice, relaxation, and yoga exercise (Appendix D). The basic philosophy of this intervention is the emphasis of the nurturing of self-kindness attitude, and non-attachment attitude towards inter-personal connectedness and letting go of self-criticism, need for control, and defensive separation in times of adversity. Short breaks will be arranged between each practice. Adjuvant to the in-session practices, participants are recommended to practice the mindful techniques every day for at least 20 minutes while keeping a record of their practice.

(c) Waitlist control group members will continue with routine care and can join either the Baduanjin or Mindful intervention after the 6-month post-intervention assessment.

Ethics

This study will be reviewed by the HKU/HA Institutional Review Board. Written informed consent will be obtained from all participants. To ensure confidentiality, codes will be used to replace names. All data collected will be kept in locked spaces and destroyed 3 years after the study ends. The study will also be registered with the Hong Kong clinical trial registry.

Measurements

Assessments pertain to areas of (i)cancer-related symptoms and symptom distress, (ii)mental health, (iii)quality of life, (iv)biomarkers, (v)mindfulness, (vi)compliance, and (vii)demographic and clinical details. Self-rated scales and salivary cortisol are administered by participants themselves while blood pressure would be measured by the trained research assistant blinded to the randomization. Measurements are taken at all time points except demographic and clinical details.

Cancer-related symptom, symptom distress and quality of life

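### The qigong versus mindfulness contrast adjusts for practice compliance, a post-randomisation outcome, so it need not estimate the total randomised difference

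*Combined protocol and SAP*

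**What the plan says.** Item 2 of Data analyses describes the only direct comparison of the two programmes. It fits multigroup conditional growth models and takes the difference between arms in the intercept of the slope factor. On covariates it adds: "Influential confounding variables such as clinical prognosis or frequency, intensity and duration of maintenance (compliance) of practice will be controlled". Nothing there marks the practice-adjusted model as a mediation, sensitivity or exploratory analysis, and no head-to-head contrast without the adjustment is described. Item 4 lists a cortisol growth curve model for all objectives but specifies no arm contrast.

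Elsewhere the document treats practice as follows.

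- **It is an outcome.** Primary objective 2 "is to examine the commonalities and differential effectiveness between two interventions on" four items, the last being "4) extended compliance". Study Hypotheses, 3(d), expects similarities and differences in "frequency and length of self-practice and long-term compliance".
- **It belongs to both programmes.** Under Intervention groups, qigong "participants are encouraged to practice Baduanjin qigong for at least 20 minutes each day"; in the mindfulness arm "participants are recommended to practice the mindful techniques every day for at least 20 minutes while keeping a record of their practice".
- **It is measured after randomisation.** Measurements (i): "Participants will record their daily duration of qigong or mindfulness meditation practice over the course of the study". The same item says the log also shows whether the habit is kept up once the sessions end.
- **Some of it follows the outcomes.** After baseline, Research design places assessments at ("ii)mid-intervention (4th week), (iii)post intervention (8th week), (iii)6 months post-intervention"), so maintenance practice is recorded after the week 4 and week 8 outcomes.

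**The concern.** A confounder of a randomised contrast would have to precede allocation. Home practice of the assigned programme cannot: it starts after allocation, and Appendix B excludes people who already practise regularly. Practice may lie on the path from programme to outcome, may share unmeasured causes with the outcome (general health, motivation), or may result from early improvement. In none of these cases does conditioning on it remove confounding.

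A slope-factor intercept in a conditional model depends on the covariates, so the sentence on control helps to define what is estimated. Primary objective 2 asks how the programmes differ in outcomes and, separately, in extended compliance. The adjusted contrast takes the second out of the first. If one practice is easier to keep up and works better for that reason, the analysis can hide it. If practice merely follows health or early improvement, the contrast can shift although practice has no effect.

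**Working it through.** **Inputs from the documents.** 189 recruited, 63 per arm; 126 evaluable, so 126/3 = 42 per arm; attrition about 33.5%; four assessments, at about months 0, 1, 2 and 8. As a check, 126/(1 - 0.335) = 189.5, which agrees with 189 to within rounding. The documents give no practice gap between arms, no practice coefficient and no expected head-to-head difference. All values for these below are assumptions, in SD units.

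**Formula.** Let A be arm (1 = the arm that practises more) and C practice, with C = δA + error. Let the individual slope be S = τA + γC + error, with γ common to both arms.

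- Contrast without C: τ + δγ, the total randomised difference.
- Contrast with C: τ.
- Shift from adjusting: -(δ × γ). It is zero if δ = 0 or γ = 0.

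| Gap δ | γ = 0 | γ = 0.1 | γ = 0.25 | γ = 0.5 |
|---|---|---|---|---|
| 0 | 0 | 0 | 0 | 0 |
| 0.2 | 0 | -0.02 | -0.05 | -0.10 |
| 0.5 | 0 | -0.05 | -0.125 | -0.25 |
| 1 | 0 | -0.10 | -0.25 | -0.50 |

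**Benefit wholly through practice.** With δ = 0.6, γ = 0.5 and τ = 0, the total is 0.6 × 0.5 = 0.30 and the adjusted value is 0. Simulation (63 per arm, 6,000 trials) gave 0.299 unadjusted and 0.000 adjusted. In two null checks with a true difference of 0.30, the contrasts agreed: 0.300 and 0.300 with a gap of 1 but no relation; 0.301 and 0.301 with a relation but no gap.

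**Power.** Take a total of 0.50, half of it through practice (0.25 + 0.5 × 0.5), and treat individual slopes as observed. Power falls from 0.61 to 0.23 at 42 per arm and from 0.79 to 0.34 at 63 per arm.

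**Shared cause, no true difference, no practice effect.** An unmeasured U enters both practice and slope with weight w. Bias = -(gap × w²). With w = 0.5 this is -0.05, -0.125 and -0.25 slope SD for gaps of 0.2, 0.5 and 1. With w = 0.3 it is -0.018, -0.045 and -0.09.

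**Outcome drives practice.** Let maintenance practice have correlation r with the slope, with a true difference of 0.50 and no other gap. The gap is then 0.5r and the coefficient r, so the adjusted value is 0.50 - 0.50r² = 0.50(1 - r²): 0.48, 0.455 and 0.375 for r = 0.2, 0.3 and 0.5.

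**Growth-model check of the shared-cause case (w = 0.5).** Assumptions: 63 per arm, random intercept SD 1, residual SD 0.5, visits at months 0, 1, 2 and 8, 33.5% random dropout, practice centred at the grand mean, common coefficients, 3,000 trials. Bias in slope SD was -0.045 to -0.053 at gap 0.2, -0.124 to -0.141 at gap 0.5 and -0.252 to -0.258 at gap 1, close to the closed form. Rejection rates at a nominal 5%, by assumed slope SD per month:

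| Gap | SD 0.05 | SD 0.1 | SD 0.25 | SD 1 |
|---|---|---|---|---|
| 0.5 | 5.7% | 7.7% | 9.8% | 10.4% |
| 1 | 8.7% | 13.5% | 19.8% | 23.8% |

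At gap 0.2 the rate was 5.4% to 6.3%. Unadjusted it was 4.5% to 5.7%.

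**Centring.** The plan does not state it. With arm-specific coefficients and uncentred practice, the intercept contrast refers to zero practice and can move even when mean practice is equal. With a mean of 2 SD in both arms, coefficients 0.3 and 0.2 and no true difference, it is -2 × (0.3 - 0.2) = -0.20.

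**The case against.** The strongest reply is that the sentence is loose. It gives examples and does not fix the centring, whether coefficients are shared, or how practice enters. Centring within each arm would return the total difference. That is correct, but such a model no longer controls for arm differences in practice, which is what the sentence says will be done. It is fair that the formula and first table describe one assumed model.

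Second, no document supports a large gap: contact hours and the 20-minute advice are the same in both arms. The highest error rates also need extreme inputs. A slope SD of 1 per month implies a month-8 outcome SD of √(1.25 + 64) = 8.1 against √1.25 = 1.1 at baseline. This stands: the rates of 20% to 24% should not be read as forecasts for this trial.

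Third, the two waitlist comparisons in item 1 carry no such adjustment and allow an indirect comparison of the programmes. No test of that kind is planned, so this softens the problem without removing it.

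Fourth, a comparison at equal practice is a legitimate question, given the interest in different entry points. It is a secondary question, however, and shared causes of practice and outcome would bias the answer.

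Finally, practice may predict dropout, so removing it might weaken the missing-at-random assumption. It can serve as an auxiliary variable for missingness without being a covariate in the contrast.

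**Conclusion.** The concern holds, and the text must be changed. The plan conditions its only described head-to-head contrast on a variable that arises after randomisation and is an outcome of the same primary objective. When practice differs by arm and is related to the slope, the controlled contrast is not the total randomised difference, whether the relation is causal, comes from a shared cause, or runs from outcome to practice.

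The size cannot be obtained from the documents and may be zero. Over the assumed gaps of 0.2 to 1 SD and coefficients of 0.1 to 0.5, the shift runs from -0.02 to -0.50 SD. This assumes a common coefficient. Exact cancellation is possible but a special case. The waitlist comparisons are outside this point, and so is adjustment for clinical prognosis if it is measured at baseline.

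**What to change.** In Data analyses, item 2, remove the practice measures from the list of controlled variables. Suggested text:

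> The main head-to-head contrast is the randomised one, adjusted only for variables measured before randomisation. Practice measures are analysed as outcomes under Primary objective 2(4) and are not covariates in this contrast.

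Three additions complete the change:

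- Name the method for comparing practice between arms, since Data analyses gives none.
- Keep any practice-adjusted model as a separately labelled exploratory mediation or dose-response analysis, with the centring and assumptions stated.
- If practice is expected to predict dropout, specify it as an auxiliary variable for missing data only.

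The cost is SAP wording. No new data are needed, and the practice-adjusted contrast becomes exploratory.
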